4.3.1 Pharmacy and pharmacist eligibility criteria

In NSW, the Chief Medical Officer signs an Authority for the legislative changes allowing approved pharmacists in approved pharmacies to provide the intervention (see Appendix 1a) through participation in the trial.

The ACT legislation process has been determined by the acting Chief Pharmacist in ACT. A licence application will need to be made by participating pharmacies. The licence (available via [PDF](#)) would be issued to authorise the 15 pharmacies in the ACT to participate in the trial (Appendix 14) and there will be no licence fee for participating pharmacies. Further details on the licensing can be found on the ACT website: <https://www.health.act.gov.au/businesses/medicine-and-poisons-licences-and-permits/>

Pharmacies and pharmacists recruited must meet the eligibility criteria (defined below) to participate in the trial, reflecting the criteria set by the Authority under Section 10 Poisons and Therapeutic Good Act 1966 [Clauses](#) 170 and 171 of the Poisons and Therapeutic Goods Regulation 2208 (please see the NSW Health Authority (Appendix 1) signed by the Chief Medical Officer) and the ACT licence (Appendix 14). All pharmacies that have expressed an interest to participate will be sent a copy of the Authority or provided the ACT licence. There are minor differences in wording of criteria between the NSW Health Authority and ACT licence. A summary is detailed below:

1. Community pharmacies

- A community pharmacy in NSW or ACT must have a service room, consulting room, or area consistent with the following (as per the Authority and licence):
 - “Ensures the room or area is not to be used as a dispensary, storeroom, staff room or retail area,
 - fully enclosed and provides adequate privacy (a divider or curtain in a dispensary, storeroom, staff room or retail area is not acceptable),
 - has adequate lighting,
 - is maintained at a comfortable ambient temperature,
 - has a hand sanitisation facility,
 - has ready access to a hand washing facility, and
 - has sufficient floor area, clear of equipment and furniture, to accommodate the person receiving the consultation and an accompanying person, and to allow the pharmacist adequate space to manoeuvre.”

Pharmacies must have access to a Pharmacist Consult form in MedAdvisor developed specifically for the trial to complete clinical record keeping for the purposes of the clinical trial assessment.

2. Pharmacists

- A community pharmacist holding general registration employed or engaged in an eligible participating pharmacy in NSW and ACT and:
 - who has successfully completed the following training:
 - Australasian College of Pharmacy modules on dermatology conditions; or
 - Pharmaceutical Society of Australia module on dermatology conditions; and
 - Modules developed by the University of Newcastle for the clinical trial.

A pharmacist is eligible to participate if they hold general registration as a pharmacist with the Australian Health Practitioner Regulation Agency (AHPRA). Pharmacists with provisional registration (intern pharmacists) and pharmacists with conditions on their registration are not eligible to participate in the trial. The pharmacy must have at least one eligible pharmacist who is willing to provide their voluntary consent to

participate, for the pharmacy to be eligible, and that there is always a pharmacist available, within reason, to deliver the service during all opening hours of the pharmacy.

Prior to service delivery, pharmacists will be prepared through an educational program. This program consists of the following training modules:

- Australasian College of Pharmacy (ACP) modules on Impetigo, Atopic Dermatitis, Mild Plaque Psoriasis and Herpes Zoster; or
- Pharmaceutical Society of Australia (PSA) module on dermatology conditions (Mild Plaque Psoriasis, Impetigo, Herpes Zoster and Atopic Dermatitis); and
- Modules developed by the University of Newcastle for the clinical trial (Introduction, Clinical Practice Guidelines, Antimicrobial Resistance and Stewardship for Impetigo and Herpes Zoster, and Introduction to Prescribing).

Completing this educational program is expected to take between 8 and 10 hours in total.

The modules developed by the University of Newcastle will be provided free to participants, whilst the Australian College of Pharmacy Practice and the Pharmaceutical Society of New South Wales will be offered free to members of the respective organisations, or for non-members there will be a charge associated. MedAdvisor will also provide training to the participating pharmacists as part of the contractual agreement with the University of Newcastle on how to use the software. The study specific training modules will be completed by pharmacists to ensure efficiency in the consultation process, patient consent, recruitment of patients, timely referral, and quality data collection.

The training verification process for pharmacists will be as follows:

- Once pharmacists have completed either the ACP or PSA courses, they will need to upload their certificates of completion during completion of the University of Newcastle modules.
- During the completion on the University of Newcastle modules, pharmacists will complete a self-assessment component after which details of the pharmacist's full name, their AHPRA number and email address.

4.4 Participant (patient) recruitment

A flyer will be developed and approved by the NSW Ministry of Health to inform patients of the service and will be displayed in a prominent location in each participating pharmacy (Appendix 15). Patients will be opportunistically recruited in participating community pharmacies. Consecutive patients will be identified on presentation to the community pharmacy with symptoms suggestive one of the four skin conditions and either: presenting symptoms requesting advice or self-selecting a product for symptoms for the conditions included in this study - Impetigo, Atopic Dermatitis, Mild Plaque Psoriasis and Herpes Zoster. If meeting the below inclusion criteria, the pharmacist will make an offer to the individual to participate in the study. Patients will be asked for their informed consent to participate in the study via an electronic signature (Appendices 16-19).

4.4.1 Participant (patient) consent

All participants will require informed consent. The pharmacist will provide the participant with a location specific QR code for scanning on their mobile phone. This will open a secure webform hosted by The George Institute. The participant will then enter their details (name, email, phone number, date of birth, postcode, suburb and the name of their regular General Practitioner if they wish this communication to be passed to them), personal contact preference and be asked to review and tick the boxes. They will then provide a finger signature on a signature panel on the screen and click submit for secure submission to The George Institute. The participant will be sent an SMS or email confirmation message with a validation code which they will provide to the pharmacy. Alternatively, the pharmacist can provide a device and assist the patient to consent.

If participants wish to withdraw from the study once it has started, they can do so at any time without having to give a reason. Withdrawing from the study will not affect their relationship with their employers, professional organisations, care providers or receipt of any care or treatment. Participants wishing to withdraw should notify the research team via the email address provided to them in the consent form. Once a

participant decides to withdraw from the study, no further information will be collected from them, and their information/data will be removed from study records and will not be included in the study results.

4.4.2 Participant (patient) inclusion criteria

The age requirements for participation vary depending on the condition:

- Mild to moderate atopic dermatitis, 6 months to 65 years old
- Herpes Zoster (Shingles), 18 years and older
- Impetigo, 12 month or above
- Mild plaque psoriasis, 18 years and older

If an individual meets the age requirements for their condition, the pharmacist may offer them participation in the trial and provide a consultation. This consultation could lead to (i) referral to a medical professional and/or (ii) an appropriate management and treatment plan, which may involve pharmacotherapy, supportive therapy, and general advice.

Specific referral criteria for each of the four skin conditions are outlined in the co-designed clinical guidelines for NSW/ACT in Appendix 2. These guidelines clearly define when and to whom timely referral should be made.

4.5 Intervention description

The intervention is multicomponent.

4.5.1 Pharmacist-patient consultation

The pharmacist will undertake a structured consultation with the patient in the community pharmacy, anticipated to take 10-20 minutes, applying the co-designed clinical guidelines (Appendix 2) which considers the recommendations from the Australian Therapeutic Guidelines.

The intervention is provided under the NSW Health Authority (Appendix 1) allowing participating NSW pharmacists to supply medications as part of the trial. For the ACT, a free-of-charge [discretionary licence](#) will be approved to participating pharmacies.

4.5.2 Implementation strategy

There will be follow up training and ongoing support as part of a translational/implementation strategy. Additional instore training may be required (such as the use of the MedAdvisor software, the clinical assessment process, etc). Practice change facilitators (PCFs) will visit pharmacies to provide any required training, ongoing support, answer any queries, ensure quality data is being collected, and collect implementation data. Since this training will be face-to-face or through remote contact, the PCFs can tailor that to the specific pharmacists/pharmacy.

4.5.3 Considerations for the delivery of the intervention

Cost to patients

NSW - The cost of the consultation with patients (\$35) will be paid for by the NSW Government to pharmacies, irrespective of the outcome of the consultation. The patient will meet out of pocket expenses for any medicines or products provided.

ACT - The cost of the consultation will be paid for by the patient receiving the service to pharmacies, irrespective of the outcome of the consultation. The patient will also meet out of pocket expenses for any medicines or products provided.

The approved pharmacist will be trained to clearly communicate all costs that may be involved in receiving treatment at the earliest point possible and throughout the consultation. Medicines will not be subsidised by the Pharmaceutical Benefits Scheme (PBS). A statement has been included in the patient information statement and consent form so that the patient is fully informed of any costs associated with receiving the service.

Financial support to NSW pharmacies

The NSW Ministry of Health, sponsor of the trial, will provide financial support to NSW pharmacies who consent to participate in the trial, including:

- a one-off 'practice allowance' of \$500. The financial support will offset technology infrastructure costs associated with participation in the trial.
- a \$35 fee for administration and data recording per consultation, irrespective of the outcome of the service, to offset your time devoted to the trial. Please note that patients will be required to meet the costs of any medications, if supplied.

The criteria for receiving these payments are that pharmacies:

- provide at least one dermatology consultation during the trial.
- have at least one approved pharmacist.
- install the MedAdvisor IT program designed for the trial.
- meet the requirements of the NSW Health Authority.

The practice allowance will be paid directly to the provider of the program and will cover all the costs associated with IT training, installation and maintenance.

The administration and data recording fee per consultation will be paid retrospectively on a 3 monthly cycle.

The study will be completed when 22,857 consults are reached or on 28 February 2025, whichever occurs first.

Cost to ACT pharmacies for IT program

Pharmacies must have access to a Pharmacist Consult form in MedAdvisor developed specifically for the trial to complete clinical record keeping for the purposes of the clinical trial assessment. This program incurs a cost of \$500 for participating ACT pharmacies for the duration of the trial. This cost is not covered by ACT Health.

Cost of pharmacist training

The modules developed by the University of Newcastle will be provided free to NSW and ACT participants, whilst the ACP and the PSA online learning modules will be offered free to members of the respective organisations, or for non-members there will be a charge associated.

Legislative considerations

NSW - The legislative approval required for the trial has been developed and is in the process of execution by the NSW Ministry of Health (Appendix 1).

ACT - The ACT legislation process has been determined by the acting Chief Pharmacist in ACT. A licence application will need to be made by participating pharmacies in ACT. The discretionary licence will be issued free to authorise the 15 pharmacies in the ACT to participate in the trial (Appendix 14).

Professional indemnity for pharmacists

Pharmaceutical Defence Limited (PDL) is the major provider of professional indemnity and will cover pharmacists as part of their normal indemnity for delivery of this service as per previous two trials. Guild Business will cover the liability from the perspective of the pharmacy premises. The pharmacy and

pharmacists consent forms have been amended to provide consent for the researchers to pass the names and addresses of the participants in the study for the purposes of indemnity cover.

4.6 Data sources

4.6.1 Community pharmacy data

During implementation of the intervention, information on health service delivery and program activities will be routinely captured in a case registration form by community pharmacists using the MedAdvisor application which is built into pharmacy software systems. For the purposes of evaluation and study participants will be assigned a unique study identification number, which will replace personal data sent to the trial team. The list of data that will be collected in these extracts is presented in Table 3.

Table 3: MedAdvisor data collection form included in the prescription software

Patient information	Type of field
Surname	Free text
First Name	Free text
Middle Name	Free text
Address	Free text
Suburb	Free text
Postcode	Free text
State	Drop down
Mobile	Free text
Phone number	Free text
Email	Free text
DOB	Date picker
Sex assigned at birth	Drop down
Gender	Drop down
Medicare number	Free text
Medicare expiry	Free text
DVA	Free text
Main language spoken at home	Free text
Aboriginal and/or Torres Strait Island Status	Drop down
Emergency contact Full name	Free text
Emergency contact Number	Free text
Pharmacist details	Type of field
Consultation date	Date picker
Pharmacist	Drop down
AHPRA number	Free text
Consent	Type of field
Please note age restrictions per service.... The age requirements for participation vary depending on the condition: - Mild to moderate atopic dermatitis, 6 months to 65 years old - Herpes Zoster (Shingles), 18 years and older - Impetigo, 12 month or above - Mild plaque psoriasis, 18 years and older	Text
Participants are required to provide e-consent using their mobile phone. If the patient does not have a mobile device, the pharmacy must provide a device to complete the consent.	Text

Patient has provided e-consent to participate. Consent pertains to this service and collection of their personal information.	Checkbox
Enter the e-consent validation code:	Numeric
Medical and social history	Type of field
Past medical history	Free text
Past surgical history	Free text
Medications from dispense	Table display per dispense record
Current medications	Free text
Allergies and known adverse medication reactions	Free text
Smoking history (including vaping)	Drop down
Alcohol history	Drop down
Standard drinks per day on typical drinking day	Numeric
Recreational drugs	Free text
Relevant family history	Free text
Relevant sexual activity	Free text
Relevant work, hobbies and other information	Free text
Risk factors for referral or treatment	Type of field
If yes to any risk factor, you must provide additional insight during the objective assessment below.	Free text
Is the patient currently pregnant or planning to do so?	Radio buttons
Is the patient currently breastfeeding?	Radio buttons
Does the patient have high blood pressure?	Radio buttons
Is the patient overweight?	Radio buttons
Does the patient have diabetes?	Radio buttons
Does the patient have hepatic impairment?	Radio buttons
Does the patient have renal impairment?	Radio buttons
Does the patient have a fever?	Radio buttons
Clinical Service	Type of field
Presenting symptom (up to four)	Look up to symptom list
Subjective assessment	Free text
Objective assessment	Free text
Diagnosis	Free text
Treatment and plan	Free text
Supporting files and images	NA
Prescribe medication	Type of field
Drug name	Drop-down menu
Generic name	System data
Instructions	Free text
Quantity	Numeric
Created date	System data
Item strength (drug potency)	System data
Reason for prescribing	Free text

Administration route	Drop-down menu
Drug status	Drop-down menu
Notes	Free text
Notifications and referrals	Type of field
Who do you want to notify/refer to?	Drop down
Type of communication	Drop down
Discipline	Auto populate
Subject	Auto populate
Body of the letter	Auto populate
Attached all consultation details to the message as a PDF	Radio buttons
Send secure message	Radio buttons
Download PDF	Drop-down menu
Sent time	System data
Created time	System data
Consultation outcome	Type of field
Consultation length	Drop down
Clinical Service Type	Drop down
Review Clinical Guidelines	Link
Does the patient have a regular GP?	Radio buttons
Consultation summary: (at least one of them must be marked):	
Prescribed clinical trial medication	Check box
Did the patient decide not to purchase the medicines or products recommended as part of this consultation?	Radio buttons
If Yes, please provide further details	Free text
Over the counter treatment	Check box
Non-pharmacological management	Check box
Counselling and education	Check box
No intervention	Check box
Other (please specify)	Check box
Other text	Free text
Referrals - Reason	Type of field
Referral made - Referred to a GP as required by clinical guidelines 'red flag' or 'refer when' criteria	Check box
Referral made - Referred to an Emergency Department as required by clinical guidelines 'red flag' or 'refer when' criteria	Check box
Referral made - Patient may have a condition outside the scope of the trial	Check box
Referral made – Patient may require further investigation or tests, including pathology	Check box
Referral made - Patient may require treatment outside the scope of the trial	Check box

4.6.2 Participant (patient/carer) self-reported data from follow-up

Those assessed as eligible to participate in the trial will be followed up at different time frames depending on the condition. The follow up will include a brief survey administered by The George Institute either via SMS message or email with a link to a case report form using George Data Systems (GDS). Information will be collected on the primary outcome measure of symptom resolution/relief rate, any additional care provided, changes to treatment, service satisfaction and overall experience of care. Basic demographic (educational level, employment status, cultural status) and clinical information (condition, reason for consult, symptom description, other professional visits and other medications use) will also be captured. Appendix 20 provides the case report form for patient follow-up.

The follow up survey will be sent to patients by SMS and/or email, 7 or 14 days after the consultation depending on the condition. Up to 3 reminders will be sent to all patients that do not complete the survey at two, four and six days after the initial sending date. Patients that do not complete the survey after these reminders will be assumed as lost to follow up and will not be contacted further.

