The study will use a cohort study design to assess the clinical and economic impact and implementation of the intervention in NSW and ACT. Pharmacies will be onboarded from June 2024 to September 2024. This is due to administrative processes associated with MedAdvisor program installation, and the numbers of pharmacies that can be onboarded will be batched over this time. The study will be completed when 22,857 consults are reached or on 28 February 2025, whichever occurs first.

The intervention is multicomponent including Pharmacist training and support, and a Pharmacist-patient consultation, using an IT program, applying clinical guidelines. Pharmacies and pharmacists must meet the criteria of an 'approved pharmacy' and an 'approved pharmacist' outlined in the NSW Health Authority (Appendix 1), or a licence in ACT, to participate.

The 'approved pharmacist' will follow clinical practice guidelines originally developed by Queensland Health (Appendix 2). These guidelines have been through a co-design process (part of a separate low-risk ethics submission approved by HREC – University of Newcastle - H-2023-0448) and their content validated by dermatologists, GPs and NSW Health. These guidelines include a process for the pharmacist to make clinical decisions, and refer to other health professionals, particularly general practitioners.

The 'approved pharmacist' must complete the:

- Australasian College of Pharmacy modules on dermatology conditions; or

- Pharmaceutical Society of Australia module on dermatology conditions; and
- Modules developed by the University of Newcastle.

Pharmacists and pharmacies will be provided follow up support as part of a translational/ implementation strategy. Practice change facilitators will visit/contact these pharmacies during the study to provide ongoing support, answer any queries, ensure quality data is being collected, and collect implementation data. Pharmacies will be divided into low, medium and high contact, and this will depend on the number and nature of consultations delivered throughout the trial period.

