4.1 Study hypothesis

The study hypothesis is that the community pharmacy delivered services for four skin conditions will: (1) achieve high rates of implementation and adherence to treatment protocols; (2) result in self-reported symptom resolution/relief rates at various time interval depending on the condition; and (3) not be associated with safety risks.

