4.9 Outcomes

Primary outcome

The primary outcome will be symptom resolution/relief (completely resolved, improvement, no improvement or worsening) (based on self-report at various time frames at follow up depending on the condition). This will be a composite measure based on patient self-reported data. As symptom resolution/relief time can be different for each of the four conditions, follow-up periods according to the clinical practice guidelines will be:

- 7 days for Impetigo, Psoriasis and Herpes Zoster (Shingles)
- 14 days for Atopic Dermatitis

Secondary outcomes

Secondary outcomes will be:

- Types of medication supplied for each condition by pharmacists. This is a participant specific outcome.
- Adherence rates to treatment protocol. This is a pharmacy-specific outcome.
- Numbers of patients supplied medications by pharmacists. This is a participant specific outcome.
- Numbers of patients provided self-care advice. This is a participant specific outcome.
- Numbers of patients referred to another health professional. This is a participant specific outcome.
- Reasons for patient referral to another health professional. This is a participant specific outcome.
- Estimated duration of consultation. This is a pharmacy specific outcome.
- Patient follow-up rate. This is a participant specific outcome.
- Patient adverse events. This is a participant specific outcome.
- Patient experience. This is a participant specific outcome.
- **Safety outcomes:** Patient-reported adverse events defined as any unfavourable and unintended sign, symptom or disease associated with the use of a medicine, which does not necessarily have to be caused by that medicine (Appendix 25).
- **Implementation outcomes**
 - Patient and provider program participation rates
 - Patient demographics (gender, DOB, education, employment status)
 - Numbers of patients per pharmacy assessed as eligible for pharmacy medication supply.
 - Numbers of patients supplied medication by pharmacists.
 - Estimated duration of consultation
 - Estimated time to complete all service requirements.
 - Adherence rates to treatment protocol
 - Prescriptions for first-line medications for the four skin conditions /Total medication prescriptions for the four skin conditions
 - Classification of appropriateness of medications for the four conditions as aligned with clinical practice guidelines.

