4.10.1 Quantitative analysis

Descriptive statistics will be calculated for all study variables. Continuous variables will be reported using the appropriate measure of central tendency. Categorical variables will be summarized as proportions. Analyses will be conducted using SAS and R. The primary and secondary outcomes will be analysed with multivariable regression models adjusted for age). Sub-group analyses will be conducted to examine variation in outcomes for the cohort to assess a range of demographic and clinical characteristics.

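### The resolution/relief rate describes only patients who answer one SMS/email survey, and adjusting for age alone leaves it open to non-response bias that can exceed its sampling error

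*Protocol*

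**What the plan says.** Section 4.9 defines the primary outcome as symptom resolution/relief in four categories and adds: "This will be a composite measure based on patient self-reported data". Section 4.6.2 describes how it is collected: "The follow up survey will be sent to patients by SMS and/or email, 7 or 14 days after the consultation depending on the condition". On non-completers it says: "Up to 3 reminders will be sent to all patients that do not complete the survey at two, four and six days" after first sending, and then: "Patients that do not complete the survey after these reminders will be assumed as lost to follow up and will not be contacted further".

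The pharmacy data form (section 4.6.1, Table 3) covers the consultation and has no field for outcome at follow-up, so no second source of the primary outcome is described.

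The design in section 4.2 is a cohort, and no comparator group is described. The clinical part of the hypothesis in section 4.1 is that the service will "result in self-reported symptom resolution/relief rates at various time interval depending on the condition", which is an absolute rate.

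Section 4.10.1 gives the analysis: "The primary and secondary outcomes will be analysed with multivariable regression models adjusted for age". It adds descriptive statistics and sub-group analyses. Section 4.9 also lists among the secondary outcomes: "Patient follow-up rate. This is a participant specific outcome".

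**The concern.** Followed as written, the plan produces a rate among responders. With no second group, a distortion from selective response cannot cancel out in a comparison; it goes straight into the reported figure. Age adjustment deals only with response that varies by age. It does nothing where response differs by condition, by treatment versus referral, by whether the product was bought, by language or by place.

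Most of those variables are recorded at the consultation for responders and non-responders alike. Sections 4.7.1, 4.7.2 and 4.8 show that the consult record reaches the research team with the study ID and that the survey carries the same ID, so the two can be linked. The stated method therefore uses less than the available data allow.

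At stake is how far the clinical result under objective 2 can be read as applying to patients managed by the service rather than to those who replied. A larger cohort narrows the interval but does not reduce the bias.

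**Working it through.** **Inputs from the Protocol.** The number of consults N is at most 22,857, from section 2: "The study will be completed when 22,857 consults are reached or on 28 February 2025, whichever occurs first". No response rate, expected resolution/relief rate or precision target is given, so no figure of the plan's own can be reproduced here.

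**Assumptions.** The four categories are collapsed to one proportion. All N consults are sent the survey. Response rate r is 30%, 50%, 70% or 90%. The rate p among responders is 80%, with 70% and 90% as alternatives. The gap d (responders minus non-responders, left after age adjustment) is 5 or 10 points. The sign of d is unknown; only the size matters here.

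**Formulas.**
- Half-width of the simple 95% interval: h = 1.96 × √(p(1 − p)/(N r))
- Bias of the responder rate against all patients surveyed: b = (1 − r) × d
- Gap at which bias equals the half-width: d* = h/(1 − r)
- Worst/best bounds: r p to r p + (1 − r)

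**Example, r = 50%.** h = 1.96 × √(0.16/11,428.5) = 0.73 points. With d = 10, b = 0.5 × 10 = 5.0 points, and 5.0/0.73 = 6.8 half-widths. d* = 0.73/0.5 = 1.5 points. Bounds: 0.5 × 80% = 40%, and 40% + 50% = 90%.

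**Results at N = 22,857 and p = 80%** (gaps, half-widths and bias in percentage points):

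| r | h | d* | Bias at d = 5 (in half-widths) | Bias at d = 10 (in half-widths) | Worst/best bounds |
|---|---|---|---|---|---|
| 30% | 0.95 | 1.4 | 3.5 (3.7) | 7.0 (7.4) | 24% to 94% |
| 50% | 0.73 | 1.5 | 2.5 (3.4) | 5.0 (6.8) | 40% to 90% |
| 70% | 0.62 | 2.1 | 1.5 (2.4) | 3.0 (4.8) | 56% to 86% |
| 90% | 0.55 | 5.5 | 0.5 (0.9) | 1.0 (1.8) | 72% to 82% |

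Over r of 30% to 70%, p of 70% to 90% and d of 5 to 10 points, the bias is 2.1 to 9.9 half-widths.

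**Where the multiple shrinks** (p = 80%):
- Small gap: N = 22,857, r = 70%, d = 2 gives b = 0.6 against h = 0.62, about 1.0 half-width.
- Fewer consults: N = 2,000, r = 70% gives h = 1.96 × √(0.16/1,400) = 2.10. Then d = 5 gives 1.5/2.10 = 0.7 and d = 10 gives 3.0/2.10 = 1.4 half-widths.
- A condition with 500 consults: r = 50% gives h = 1.96 × √(0.16/250) = 4.96, and d = 10 gives 5.0/4.96 = 1.0 half-width.
- Clustering by pharmacy: a design effect of 4 doubles h and halves every ratio.

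In all these cases the bias in points is unchanged for a given r and d. Only the interval is wider.

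**The case against.** The strongest objection is that methods for missing outcomes commonly belong in the statistical analysis plan, which is not at hand, and that section 4.10.1 is a summary that does not rule out weighting. This stands in part: the absence of a missing-data method from the Protocol is not itself an error. The point rests on what the Protocol does fix, namely one channel, no further contact, no second outcome source and one named covariate, and on a better method being available from linked data.

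The sentence on age adjustment ends in an unmatched bracket, so words may have been lost, and a multivariable model sits oddly with a single covariate. That is fair, but age is the only variable the text names. The sub-group analyses do not help, because each still describes responders only.

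The plan does something about non-response: three reminders, and follow-up rate as a secondary outcome. This limits and measures non-response but does not correct for it.

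Three stronger readings are tempting and not supported:
- A reader might infer that the bias is many times the confidence interval. That depends on a response rate and a gap that the Protocol does not give. The 22,857 is also a ceiling, and the simple half-width ignores clustering.
- A reader might infer that adverse event rates are affected in the same way. Section 4.9 calls them patient-reported, but section 4.6.2 does not list them among the survey items, and Appendices 20 and 25 are not shown.
- A reader might infer that the plan claims a narrow precision. It states none.

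Finally, weighting removes only the bias explained by recorded variables. If response depends on the outcome itself, bias remains, and nothing here measures how much weighting would recover.

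**Conclusion.** The point holds in conditional form. The resolution/relief rate, as planned, is a responder rate in a single cohort, and adjustment for age does not protect it from response that differs on other grounds. At the full 22,857 consults and an assumed 80% rate, a gap of about 1.4 to 2.1 points is enough for bias to match the simple 95% half-width at response of 30% to 70%; at 90% response it takes about 5.5 points. Gaps of 5 to 10 points at 70% response or less make the bias several half-widths. It is near or below one half-width in other settings, such as 90% response with a 5-point gap, a 2-point gap at 70% response, or some estimates from a small single condition or after a stop on the end date.

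These figures rest on assumed response rates, outcome rates and gaps, independent patients and a binary outcome. This is an inexpensive improvement that should be made, not a demonstration that the result will be wrong.

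**What to change.** In section 4.10.1, state that the resolution/relief rate will be estimated by condition for patients sent the follow-up survey, leaving out those who withdraw, since section 4.4.1 removes their data. Weight each responder by the inverse of a modelled response probability. Build that model from consult-record variables: age, sex, condition, treatment or referral, declined purchase, and language and postcode. The last two are free text in Table 3 and need coding first. Allow for clustering by pharmacy.

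Beside the weighted rate, report the unweighted responder rate, the response rate by condition and the worst/best bounds. Say plainly that weighting corrects only non-response explained by recorded variables. Apply the same treatment to adverse event rates only if they are collected in this survey.

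The cost is some coding and analysis work on data already collected, and a wider interval. No further contact with patients is needed.
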